## 1.0 Study Summary

Study Title	The Role of Contrast Enhanced Ultrasound to Diagnose Children with Appendicitis
Study Design	Single institution non-randomized clinical trial
Primary Objective	Determine the efficacy of contrast enhanced ultrasound (CEUS) in improving the diagnosis of acute appendicitis in children
Secondary Objective(s)	
 
• Utility of CEUS in making a definitive diagnosis of acute appendicitis
 
• Utility of CEUS in decreasing Rates of CT scan utilization
 
• Outcomes of patients who undergo CEUS for appendicitis
 
• Negative appendectomy rates
 
• Costs
 

Research Intervention(s)/Investigational Agent(s)	Lumason (sulfur hexafluoride lipid-type A microspheres) injectable suspension
IND/IDE #	N/A
Study Population	Children between the ages of 8 and 17
Sample Size	250 subjects
Study Duration for Individual Participants	30-60 minutes
Study Specific Abbreviations/Definitions	
CEUS- contrast enhanced ultra sound      CT- computed tomography      MRI- magnetic resonance imaging      CMH- Children's Mercy Hospital      DSDR- Department of Surgery Data Repository      DOB- date of birth      MRN- medical record number      OSH- outside hospital      PAS- pediatric appendicitis score      LAR- legally authorized representative      IV- intravenous      PI-principal investigator      ICU- intensive care unit      P/A- permission/assent      ED Emergency Department

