## 2.0 Objectives

- 2.1 The main objective of this study is to determine the efficacy of Contrast Enhanced Ultrasound (CEUS) in improving the diagnoses of acute appendicitis in children.
- 2.2 We hypothesize that CEUS can be used effectively to make a definitive diagnosis when gray-scale ultrasound is inconclusive.

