## 4.0 Study Endpoints

4.1 The primary endpoint is the proportion of patients for whom the appendix is enhanced by CEUS when using the same diagnostic criteria as gray scale ultrasound. Lumason will be considered effective if the sensitivity of grayscale ultrasound is enhanced in more than 50% of images as determined by the blinded interpreting pediatric radiologist.

Secondary endpoints include:

- Utility of CEUS in making a definitive diagnosis of acute appendicitis
- Utility of CEUS in decreasing rates of CT scan utilization
- Negative appendectomy rates

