5.3 N/A

## 6.0 Procedures Involved

- 6.1 This will be a single-center non-randomized trial that will add to our institution's current diagnostic algorithm one CEUS to subjects whom are clinically suspicious for acute appendicitis. Currently, a gray-scale abdominal ultrasound is performed to help establish the diagnosis. When the results of the gray-scale abdominal ultrasound are inconclusive, the treating physician may choose to refer the patient for a CT scan in order to establish a definitive diagnosis. Our study does not look to alter that process.
- 6.2 For those who consent to study participation, we propose obtaining a CEUS after the initial gray-scale ultrasound. Once the initial ultrasound is complete, the contrast Lumason® (sulfur hexafluoride lipid type-A microspheres) will be administered through an already existing IV catheter by an MD, RN or a radiology technologist trained and certified to administer the Lumason® contrast agent, and

an abdominal scan will be completed. The patient will then continue with standard of care treatment per his treating physician. The CEUS image will be read at a future time by a CMH radiologist blinded to the results of the gray scale ultrasound and CT if one was obtained as these will be used for comparison.

6.3

- Lumason will be administered by radiology personnel (radiologist, US technologist, or Sedation RN). Subjects will be monitored during the entirety of the procedure. Once the study procedure has been completed, patients will continue to go through the standard of care process and return to the ED (Emergency Department) or floor while they await the results of their gray-scale ultrasound and CT, if one was obtained. ED/ floor staff will continue to monitor patients for any adverse events.
- Lumason (sulfur hexafluoride lipid-type A microspheres) is the investigational product. The recommended dose of Lumason for children is 0.03 mL/kg up to a maximum dose of 2.4mL injected into a peripheral intravenous catheter. See individualization of dose below.

1. Follow the Lumason injection with a flush of 5 ml of 0.9% Sodium Chloride Injection, USP.
2. The maximum total dose for children as listed in the package insert should not exceed 2.4 mL in any 10-minute period. For this study, over any 10-minute period we intend to administer the approved dose of 0.03 mL/kg up to a maximum of 2.4 mL.

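### The secondary endpoint on lowering CT use cannot be met by this design, because the CT decision is left unaltered and CEUS is read later

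*Protocol*

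**What the plan says.** The synopsis (protocol section 1.0) gives as one of five secondary objectives "Utility of CEUS in decreasing Rates of CT scan utilization". Section 4.0 repeats it as one of three secondary endpoints: "Utility of CEUS in decreasing rates of CT scan utilization". Neither place gives a metric, a denominator or a comparator.

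Section 6.0 sets out the procedures:

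- **CT decision (6.1).** After an inconclusive gray-scale scan, "the treating physician may choose to refer the patient for a CT scan". On this pathway the protocol says "Our study does not look to alter that process".
- **CEUS read (6.2).** "The CEUS image will be read at a future time by a CMH radiologist", who is "blinded to the results of the gray scale ultrasound and CT if one was obtained as these will be used for comparison". After the scan the child goes on with standard care.
- **Results awaited (6.3).** Children return to the emergency department or floor "while they await the results of their gray-scale ultrasound and CT, if one was obtained". CEUS is not among the results awaited.

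Section 2.2 states the hypothesis that "CEUS can be used effectively to make a definitive diagnosis when gray-scale ultrasound is inconclusive". Section 6.4 lists the data collected, including US, CEUS and CT findings, pathology and intraoperative findings.

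**The concern.** The endpoint is worded as an effect: CEUS lowers the rate of CT. For CEUS to have that effect, its result must be available to whoever orders the CT, before the order. The procedures make no provision for this. A CT rate calculated from enrolled children would then be the rate under usual care, in a convenience sample (section 20.2), among children who happened also to have a CEUS.

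Avoiding radiation from CT is a stated motive in the background (section 3.1), so this endpoint is likely to attract attention. A standard-care CT rate, perhaps set beside an older institutional rate, could be reported as a benefit of CEUS when the design gives no basis for that.

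**Working it through.** The protocol states no baseline CT rate, target reduction or power for this endpoint, so there is no figure to reproduce. The check is whether a CEUS result can reach the CT decision under section 6.0.

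**Step 1: who decides on CT, and on what.** The treating physician decides, on an inconclusive gray-scale result (6.1). The study does not intend to change this.

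**Step 2: when CEUS is read.** It is read later, by a reader blinded to CT if there was one (6.2). Blinding to CT matters only if a CT may already exist at the time of the read, so the read is planned for after the CT decision.

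**Step 3: whether the read is fed back.** Care after the scan is standard care (6.2), the results awaited are gray scale and CT (6.3), and no step sends the CEUS read to the treating team. CEUS reads planned to reach that team before the CT decision: 0 of up to 250.

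**Step 4: whether a comparator could rescue the endpoint.** The trial is single-centre and non-randomized, and CEUS is planned for every consenting child. A statistical analysis plan could name a historical CT rate. A difference from it still could not be attributed to a read that clinicians did not receive.

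**Step 5: what the data can support.** The hypothesis in section 2.2 can be carried to the CT question within patients: among children with inconclusive gray scale who had a CT, how often was the blinded CEUS read definitive and correct? The size of that group, n, is not given. I assume 25, 50 or 100 children (10%, 20% or 40% of 250).

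The exact (Clopper-Pearson) 95% limits for x of n are: lower = the 0.025 quantile of Beta(x, n − x + 1); upper = the 0.975 quantile of Beta(x + 1, n − x).

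| Definitive and correct | n = 25 | n = 50 | n = 100 |
|---|---|---|---|
| 40% | 10/25: 21.1–61.3% | 20/50: 26.4–54.8% | 40/100: 30.3–50.3% |
| 60% | 15/25: 38.7–78.9% | 30/50: 45.2–73.6% | 60/100: 49.7–69.7% |
| 80% | 20/25: 59.3–93.2% | 40/50: 66.3–90.0% | 80/100: 70.8–87.3% |

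Widths are about 40, 28 and 20 points at 40% or 60%, and about 34, 24 and 16.5 points at 80%.

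For reads that are definitive but wrong, the upper limit with none observed is 1 − 0.025^(1/n): 13.7%, 7.1% and 3.6%. With 4% observed the intervals are 0.1–20.4% (1/25), 0.5–13.7% (2/50) and 1.1–9.9% (4/100).

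These counts and proportions are illustrative. They show what the replacement endpoint could deliver; the defect in steps 1 to 4 depends on none of them.

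**The case against.** The strongest reply is that utility can mean potential utility. Section 4.0 does not say that the observed CT rate is the metric, section 6.2 uses gray scale and CT for comparison with the CEUS read, and section 2.2 targets inconclusive gray scale. Read together, these allow the question of whether CEUS could have replaced CT, and the working definition could sit in an analysis plan that is not shown. This partly stands: the intention may well have been that. But the wording speaks of decreasing rates, which is an effect on CT use, and if potential utility is meant, the protocol needs to say so.

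A second reply is that treating staff might see CEUS images informally. Section 18.1 suggests that better images may inform treating providers. This is not ruled out, but it is neither planned nor listed among the data recorded, and it conflicts with the deferred read. An endpoint cannot rest on it.

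Third, the point is limited in weight. It concerns a secondary endpoint, and the primary endpoint, sample size and safety plan are unaffected. The count of 0 of 250 restates the procedures, and the intervals above describe the proposed replacement rather than the trial as written. All of that is fair. A simpler remedy, reporting the CT rate descriptively and nothing more, would also remove the error, though it would leave the CT question unanswered.

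**Conclusion.** The concern holds. Under the written procedures no planned CEUS read can influence the CT decision, so the observed CT rate cannot show that CEUS decreases CT use, at 250 subjects or any other number. An analysis plan cannot repair this, because the endpoint and the procedures that defeat it are both fixed in the protocol. The conclusion rests on the stated procedures alone and assumes only that they are followed. It should be corrected, but it does not threaten the main result of the trial.

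**What to change.** 1. Reword the endpoint as potentially avoidable CT: among children with inconclusive gray scale who had a CT, the proportion whose blinded CEUS read was definitive and agreed with the reference result, with an exact 95% interval. Report beside it the proportion definitive but wrong, with its interval. Take as reference pathology if operated, intraoperative findings if operated without pathology, and otherwise CT; report indeterminate CT without operation separately. Define definitive and inconclusive in the same way for CEUS and gray scale.
2. To show the selection into CT, give the number with inconclusive gray scale and no CT, and how many of them had a definitive CEUS read.
3. State that the observed CT rate describes standard care and is not evidence of a CEUS effect. The same sentence should cover the negative appendectomy rate, which is subject to the same lack of feedback.
4. As a lesser matter, reconcile the possible-benefit statement in section 18.1 with the deferred read in section 6.2.

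**Cost.** The change is to endpoint wording, plus one cross-tabulation of items already listed in section 6.4 and no new procedure. That section lists imaging findings rather than a definitive or inconclusive category, so the categories must be defined and coded.

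**Downsides.** The claim becomes CT that could have been avoided. The denominator is selected, since CT is the physician's choice. The reference differs between operated and non-operated children, CT may influence who is operated on, and CT is imperfect as the reference in those who are not. Precision is low if few have a CT.

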3. The maximum total dose for children as listed in the package insert should not exceed 4.8 mL in any one patient during the full time on study. In this study, we intend to administer a total dose in any one patient during the full time on study of 0.06 mL/kg with a maximal dose of 4.8 mL.

6.4 Data extracted from the electronic medical record will be entered into a secure REDCap database and stored in a password protected file on the CMH network. A master list containing only the assigned study ID and linking MRN will be kept in a separate REDCap instrument. All electronic files will be kept on the secure password-protected computers of the research staff and principal investigator.

Data points to be collected include the following: demographics, findings on radiology imaging (US, CEUS, and CT if applicable),

pathology, intraoperative findings, other/ comments. Reports of headache, nausea, altered taste, injection site reaction, feeling hot/ flushed, chest pain, or dizziness will also be recorded.

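### As a crude cohort rate, the negative appendectomy endpoint describes standard-care surgical selection and cannot be evidence for or against CEUS

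*Protocol*

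**What the plan says.** Protocol section 4.1 lists three secondary endpoints. The first two are worded as the utility of CEUS, for example "Utility of CEUS in decreasing rates of CT scan utilization". The third is only "Negative appendectomy rates", and section 1.0 repeats it among the secondary objectives. No numerator, denominator, comparator or success rule is attached to it. The one success rule in section 4.1 belongs to the primary endpoint.

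Section 6 fixes how CEUS relates to care:

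- Design (6.1): "This will be a single-center non-randomized trial that will add to our institution's current diagnostic algorithm one CEUS". No concurrent or historical control is stated.
- Existing pathway of gray scale, then CT if the physician chooses (6.1): "Our study does not look to alter that process".
- After the scan (6.2): "The patient will then continue with standard of care treatment per his treating physician".
- Reading (6.2): "The CEUS image will be read at a future time by a CMH radiologist blinded to the results of the gray scale ultrasound".
- Waiting period (6.3): children return to the ED or floor "while they await the results of their gray-scale ultrasound and CT, if one was obtained". A CEUS result is not among those awaited.

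Section 6.4 collects the US, CEUS and CT findings together with "pathology, intraoperative findings, other/ comments". Section 20.1 plans to correlate operative findings with the gray scale read and does not mention the CEUS read there. Section 18.1 says that better images might help the providers who treat these children.

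**The concern.** The trial's objective (section 2.1) is the efficacy of CEUS in improving the diagnosis of appendicitis. A negative appendectomy rate bears on that objective only if CEUS can influence who is operated on, or if the CEUS read enters the calculation. Section 6 rules out the first as a planned mechanism, and the endpoint as worded does not provide the second.

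A surgeon would want two counts from this trial: how many removed normal appendices CEUS had read as negative, and how many inflamed ones it had also read as negative. The second is indispensable, because a reader who calls every scan negative scores perfectly on the first. A crude rate gives neither, although the fields for both are collected.

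**Working it through.** The protocol gives no expected rate, number of operations or power for this endpoint, so there is no stated figure to reproduce. The argument is structural, and the numbers below are assumed for illustration.

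**Step 1. What enters the rate.** Usual definition: crude rate = N / (N + I), where N is the number of removed appendices with normal pathology and I the number with inflamed pathology. N and I depend on who is operated on. By 6.1 to 6.3 that decision is made under standard care, before the CEUS read exists. CEUS sensitivity and specificity appear in neither term.

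**Step 2. The same cohort under different CEUS results.** Assume N = 5 and I = 95. Let (a) be the proportion of normal appendices read negative on CEUS, and (b) the proportion of inflamed appendices read negative.

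| CEUS negative, normal | CEUS negative, inflamed | Crude rate | (a) | (b) |
|---|---|---|---|---|
| 5 of 5 | 0 of 95 | 5% | 100% | 0% |
| 5 of 5 | 40 of 95 | 5% | 100% | 42.1% |
| 0 of 5 | 0 of 95 | 5% | 0% | 0% |
| 0 of 5 | 40 of 95 | 5% | 0% | 42.1% |
| 5 of 5 | 95 of 95 (every scan called negative) | 5% | 100% | 100% |

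The crude rate is 5% (exact 95% CI 1.6% to 11.3%) in every row. Only (a) and (b) together separate the rows.

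**Step 3. Can the collected data respond to CEUS accuracy?** Take the normal share among operated children whose CEUS read was positive, with crude rate r:

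(1 − spec) × r / [(1 − spec) × r + sens × (1 − r)]

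For r = 5% and sens = spec = 90%: 0.10 × 0.05 / (0.10 × 0.05 + 0.90 × 0.95) = 0.005 / 0.860 = 0.6%.

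| Assumed r | Crude rate, any CEUS accuracy | CEUS-based, 100/100 | 90/90 | 50/50 (worthless) |
|---|---|---|---|---|
| 2% | 2% | 0% | 0.2% | 2% |
| 5% | 5% | 0% | 0.6% | 5% |
| 10% | 10% | 0% | 1.2% | 10% |

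So a figure that uses the CEUS read moves with its accuracy, while the crude rate does not.

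**Step 4. Precision of the CEUS-based figures.** With 100 to 150 operations and r between 2% and 10%, about 2 (100 × 0.02) to 15 (150 × 0.10) normal appendices are expected. If CEUS read all n of them as negative, the lower limit of the two-sided exact 95% CI is 0.025^(1/n): about 16% for 2 of 2, 48% for 5 of 5 and 78% for 15 of 15. Proportion (b) is firmer: 0 of 95 gives an upper limit of 1 − 0.025^(1/95) = 3.8%.

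**The case against.** The strongest reply is that the formula in Step 1 is not the protocol's. The bullet gives none, the plural could cover a breakdown by CEUS result, and calculation details may sit in an SAP that is not shown. This stands to the extent that the point applies to the usual crude rate, not to every possible definition. It does not remove the point: the deferred read, unchanged care and missing comparator are set by the protocol, and no SAP definition of the crude rate can make it informative about CEUS.

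Second, the proposed cross-tabulation could be reported under the first secondary endpoint, on definitive diagnosis. That is true, and it means one should not say that the question is bound to go unanswered. But the protocol does not specify that table anywhere, and the only operative correlation it describes uses gray scale.

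Third, a reader might infer that a low rate would be credited to CEUS and a high one held against it. The document does not support this. The bullet is not worded as a CEUS effect, carries no hypothesis or threshold, and in section 1.0 stands beside descriptive items such as costs. Reporting it as a description of the cohort is legitimate.

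Fourth, a reader might infer that CEUS can have had no part at all in the decision to operate. That is also too strong. Nothing explicitly blinds the treating team to the images, and section 18.1 allows that they might help. If they did, the rate could move, but with every child scheduled for CEUS and no comparator, the movement could not be attributed to it.

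**Conclusion.** The point holds in limited form. Under the procedures in section 6, the usual crude negative appendectomy rate describes surgical selection under standard care and is not evidence for or against CEUS. Its dependence on CEUS accuracy is nil if the images stay out of care, as section 6 implies, and not attributable to CEUS if they do not. This rests on reading the bullet as the conventional rate, since the protocol gives no formula. The 100 operations and the 2% to 10% rates are assumptions, and the conclusion does not depend on them.

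The endpoint is secondary and no decision hangs on it, so nothing in the primary analysis is affected. The change is still worth making: it is more than a missing definition, because the crude rate cannot serve the trial's own question, while data already collected can address it in part.

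**What to change.** 1. In section 4.1, and to match in section 1.0, label the crude rate as descriptive of standard care.
2. Add, among operated children, a cross-tabulation of the blinded CEUS read with pathology. Report the proportion of normal appendices read negative and the proportion of inflamed appendices read negative, each with an exact CI and beside the same figures for gray scale. Show inconclusive reads as their own category.
3. Amend section 20.1 so that operative and pathology findings are correlated with the CEUS read as well as the gray scale read.
4. Reconcile section 18.1 with sections 6.1 to 6.3 on whether treating providers can see the CEUS images.

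The cost is wording and one table from fields collected under 6.4. There is no new procedure and no change to care.

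Two downsides should be stated in the plan. Normal appendices will be few, so the first proportion will have a wide interval (Step 4 above). Pathology exists only for operated children, so the figures carry verification bias: they are not unbiased sensitivity or specificity for all enrolled children, and they miss false-positive CEUS reads in children who were not operated on. The comparison with gray scale needs the same caution, because the gray scale result helps to decide who is operated on and the CEUS read is not meant to.

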## 5.0 Study Intervention/Investigational Agent

5.1 Lumason (sulfur hexafluoride lipid-type A microspheres) for injectable suspension is used to prepare the ultrasound contrast agent. The single use kit contains the following three items:

- One clear glass 10mL vial containing 25mg of lyophilized powder lipid-type A, 60.7 mg of sulfur hexafluoride gas and capped with a blue flip-cap
- One prefilled syringe containing 5 mL Sodium Chloride 0.9% Injection, USP (Diluent)
- One Mini-Spike

Each vial is formulated as a 25 mg sterile, pyrogen-free lyophilized powder containing 24.56 mg of polyethylene glycol 4000, 0.19 mg of distearoylphosphatidyl-choline (DSPC), 0.19 mg of dipalmitoylphosphatidylglycerol sodium (DPPG-Na) and 0.04 mg of palmitic acid. The headspace of each vial contains 6.07 mg/mL ( $\pm$  2 %) sulfur hexafluoride, SF6, or 60.7 mg per vial.

Each prefilled syringe with 5 mL of diluent 0.9% Sodium Chloride Injection is sterile, nonpyrogenic, preservative free containing 9 mg sodium chloride per mL.

Upon reconstitution with 5mL diluent, Lumason is a milky white, homogeneous suspension containing sulfur hexafluoride lipid-type A microspheres. The suspension is isotonic and has a pH of 4.5 to 7.5; it is only for intravenous administration.

The sulfur hexafluoride lipid microspheres are composed of SF6 gas in the core surrounded by an outer shell monolayer of phospholipids consisting DSPC and DPPG-Na with palmitic acid as a stabilizer. Sulfur hexafluoride has a molecular weight of 145.9. Each milliliter of reconstituted Lumason suspension contains 1.5 to 5.6 x108 microspheres, 68 mcg SF6 (12 mcL), 0.038 mg DSPC, 0.038 mg DPPG-Na, 4.91 mg polyethylene glycol 4000 and 0.008 mg palmitic acid. The sulfur hexafluoride associated with the microspheres suspension is 45 mcg/mL. Fifteen to twenty three percent of the total lipids in the suspension are associated with the microspheres. The sulfur hexafluoride lipid microsphere characteristics are listed in Table 2:

Microsphere Characteristics	
Mean diameter range	1.5 – 2.5 $\mu\text{m}$
Percent of microspheres	$\leq 10 \mu\text{m} \geq 99\%$
Upper size limit	100.0% $\leq 20 \mu\text{m}$

5.2 The control drug used in this protocol will follow the established, approved, approved organization SOP entitled Investigational Drug Service Product Storage.

